### 10.5 Maintenance Phase

Disease evaluation will be performed every 13 weeks regardless of dose interruptions or delays (see [Section 14.4](#)). Cystoscopy and urine collection for cytology during the Maintenance Phase should be done at Week 26, Week 39, Week 52, Week 65, Week 78, Week 91, and Week 104, even if there are

missed doses or dosing delays. Every effort should be made to stay on this evaluation schedule, however, a window of one week before and up to 2 weeks after these time points is permitted (e.g., the Week 26 cystoscopy and urine for cytology may be performed from Week 25 to Week 28, but as close to week 26 as possible). The complete evaluation to determine disease status (e.g., repeat cytology, cystoscopy and biopsies if required) should be completed as soon as possible following the every 13-week timepoint. Vicinium dosing may continue during these disease evaluations in the Maintenance phase per investigator discretion. Vicinium treatment should not be given within 2 weeks of any biopsy/TURBT.

Other assessments during the Maintenance Phase are as follows:

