### **10.6 Post-Treatment Evaluation**

Subjects will return to the clinic site for a Post-Treatment evaluation 30 – 37 days after their last dose of study treatment.

The following assessments will be performed at that time

- Targeted physical examination (including weight) ([Section 16.3](#))

- Triplicate ECG obtained within 30 minutes of each other at least 3 minutes apart
- Vital signs
- Concomitant medications
- Adverse events, including SAEs
- Collection of clinical laboratory samples: blood samples for hematology and chemistry, urine samples for urinalysis
- Anti-Vicinium antibodies
- Blood or urine pregnancy test (WOCBP)
- The following are to be done if the subject has not discontinued treatment due to documented disease recurrence, progression and if they have not been performed within the past 8 weeks
  - Cystoscopy
  - Biopsy (directed). EpCAM determination by immunohistochemistry will be obtained on all positive biopsies.
  - Urine cytology

As described in **Section 15**, additional follow-up will occur for subjects with ongoing clinically significant AEs (e.g., those leading to study drug discontinuation) or SAEs assessed as related to study drug.

Subjects without a treatment failure (see **Section 14.2**) will continue to undergo evaluations for disease status (urine cytology, cystoscopy, directed biopsies) every 13 weeks until the sooner of a treatment failure or the determination of the 18-month event free survival analysis. Survival data also will be collected on subjects every 13 weeks. Once all subjects are no longer receiving study treatment and the 18-month event-free survival for the study is determined, the study will close and subjects will then be followed by their physician according to standard of care.

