3.3.9. Combining Data Across Panels

When data are combined across panels to create composite endpoints, like complete response, information will be combined in the following manner:

1. Data will be merged by visit for each subject.
2. Unscheduled and early termination data will be windowed according to the visit windows below. Additionally, data from visits where pathology, cytology, and cystoscopy are unexpected (i.e., Maintenance Month 4) will be windowed using the table below.
3. Data within a given visit window will be collapsed to the worst-case result. For example, if a subject has two central pathology assessments for a given visit one with 'CIS' and the other with 'No Tumor', the analysis result for the collapsed visit will be considered as 'CIS'.
4. The date corresponding to the collapsed visit will be the earliest observed date for the visit.

Analysis Visit	Study Days
Screening	-8 < Study Day < 1
Week 1	1 <= Study Day <= 49
Post Induction Phase	49 < Study Day <= 137
Maintenance Month 3	137 < Study Day <= 227
Maintenance Month 6	227 < Study Day <= 318
Maintenance Month 9	318 < Study Day <= 409
Maintenance Month 12	409 < Study Day <= 500
Maintenance Month 15	500 < Study Day <= 591
Maintenance Month 18	591 < Study Day <= 682

Maintenance Month 21	682 < Study Day <= 773
Long-term Follow up Month 3	773 < Study Day <= 864
Long-term Follow up Month 6	864 < Study Day <= 955
Long-term Follow up Month 9	955 < Study Day <= 1046
Long-term Follow up Month 12	1046 < Study Day <= 1137
Long-term Follow up Month 15	1137 < Study Day <= 1228
Long-term Follow up Month 18	1228 < Study Day <= 1319
Long-term Follow up Month 21	1319 < Study Day <= 1410
Long-term Follow up Month 24	1410 < Study Day <= 1501

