5.2. EFFICACY ANALYSIS

5.2.1. Primary Efficacy Endpoint

The primary outcome measure is the complete response rate in subjects with refractory /relapsed CIS or CIS plus papillary disease (i.e., cohorts 1 and 2) following the initiation of Vicinium therapy.

Patients who discontinue or die before Month 3 will be included in the denominator of the primary analysis.

For the primary efficacy endpoint analysis, the following conventions will be utilized in determining treatment failure or complete response at a given visit.

1. Subjects that have centrally read pathology findings ('CIS', 'any-grade T1', 'high-grade Ta') or centrally read cytology results ('High Grade Urothelial Carcinoma') that indicate treatment failure for a given visit will be considered to have treatment failure.
2. Subjects who met a treatment failure criterion at a previous visit are treatment failures at all subsequent visits.
3. Subjects who have discontinued the study on or prior to the visit and have missing data that would be necessary to generate response are considered non-CRs.
4. Subjects who do not meet criterion 1-3 are complete responders.

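### The 3-month response window opens on Day 50, so a clear exit evaluation in Weeks 9 to 11 with no later record is scored as a 3-month complete response

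*SAP*

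**What the plan says.** SAP section 2 makes complete response at 3 months in CIS subjects a primary endpoint. Protocol 10.3.5 and 10.4 place the evaluation after induction, with cytology in Week 12 and cystoscopy from Week 13.

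SAP 3.3.9 sets out how results are assigned to visits. Its step 2 reads "Unscheduled and early termination data will be windowed according to the visit windows below". The Post Induction Phase row is "49 < Study Day <= 137". The row before it, labelled Week 1, is "1 <= Study Day <= 49" and is not a response visit. Step 3 adds: "Data within a given visit window will be collapsed to the worst-case result".

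SAP 5.2.1 then applies four rules in order:

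1. Central pathology or cytology showing failure is a failure.
2. A failure carries forward to all later visits.
3. A subject who has left the study by the visit and lacks the data needed for response is a non-responder.
4. Everyone else is a complete responder.

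The same section says "Patients who discontinue or die before Month 3 will be included in the denominator of the primary analysis". It does not say that these subjects are non-responders.

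On exit, protocol 10.6 states: "Subjects will return to the clinic site for a Post-Treatment evaluation 30 – 37 days after their last dose of study treatment". Cystoscopy, directed biopsy and cytology are part of that visit if there is no documented recurrence or progression and they were not done in the previous 8 weeks.

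**The concern.** Rule 3 needs two conditions together: departure from the study and missing response data. A clear exit evaluation that falls inside the window supplies the data, so rule 3 does not apply and rule 4 gives a response. Keeping early leavers in the denominator is meant to be conservative, but here such a subject also enters the numerator.

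The result turns on a single day. For a subject who has left the study and has no later record, a clear exit on Day 49 falls in the Week 1 row, leaves the 3-month visit empty and gives a non-responder. The same complete result on Day 50 gives a responder. Neither subject was observed at 3 months.

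The error runs one way. Failures are captured and carried forward whenever they are found, so opening the window early can only add responders among these subjects. Neither sensitivity analysis in SAP 5.2.3 covers the case. One deals with missing central readings at a visit with an abnormal cystoscopy, and the other counts low-grade Ta as failure.

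**Working it through.** **Inputs.** Window Days 50-137 (SAP 3.3.9); exit visit 30 to 37 days after the last dose (protocol 10.6); Day 1 cytology (protocol 10.3.1); the 8-week exemption for exit tests (protocol 10.6); N=77 and the planning table (protocol 17.8, SAP 3.1).

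**Calendar.** Week w starts on Day 7(w-1)+1. Week 8 therefore starts on Day 50, Week 12 on Day 78 and Week 13 on Day 85. The window opens 85-50 = 35 days before Week 13 and 78-50 = 28 days before Week 12.

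**Who can have an exit evaluation before Day 78.** A last dose on Day L puts the exit on Days L+30 to L+37.

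- An exit on Days 50-77 needs L+37 ≥ 50 and L+30 ≤ 77, so L = 13 to 47.
- Day 1 cytology is within 8 weeks (56 days) through Day 57. For exits on Days 50-57 the protocol does not require a repeat. Without one, cytology may count as missing and rule 3 may apply.
- The clear case is therefore an exit on Days 58-77. It needs L+37 ≥ 58 and L+30 ≤ 77, so it is possible for L = 21 to 47. An on-time exit must fall there when L+30 ≥ 58 and L+37 ≤ 77, so L = 28 to 40.
- Assuming doses on days 1 and 4 of Weeks 1-6 and day 1 of later weeks, these subjects have had 6 (by Day 21) to 13 (by Day 47) of the 18 induction doses.

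**Rules applied to a clear exit on, say, Day 65 with nothing later by Day 137.** Rule 1: no failure finding. Rule 2: no earlier failure. Rule 3: data present, so not met. Rule 4: complete responder at 3 months.

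**Size.** The plan's own table comes first. The Clopper-Pearson lower limit is the 0.025 quantile of Beta(x, N-x+1), with x = 0.3N.

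| N | x | Lower limit, recomputed | Plan |
|---|---|---|---|
| 76 | 22.8 | 0.2002 | 0.200 |
| 95 | 28.5 | 0.2102 | 0.210 |
| 121 | 36.3 | 0.2201 | 0.220 |

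The table reproduces. With whole subjects at N=77:

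- 24/77 = 31.2%, lower limit 0.211
- 23/77 = 29.9%, lower limit 0.1997

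One subject adds 1/77 = 1.3 points. The SAP's primary population is Cohorts 1+2, whose size is not fixed. Cohort 1 is at least 77. The planned total of 134 includes Cohort 3, so on the planned numbers the per-subject effect in Cohorts 1+2 lies between 1/134 = 0.75 and 1.3 points.

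**The case against.** Several objections carry weight.

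**Stopping drug is not leaving the study.** Protocol 11.3 separates the two. If consent is withdrawn, no further evaluation is done, so there is no exit examination and rule 3 gives a non-responder. If only treatment stops, 13-weekly evaluation continues (protocol 10.6, 11.3, 14). The Week 13 result then falls in the same window, and the worst-case collapse overrides a clear early exit. Subjects stopped for failure or recurrence are failures under SAP 3.3.7. This stands, and it narrows the group to those who attend the exit visit and have no later record by Day 137. A reader might infer that anyone stopping in Weeks 2 to 7 with a clear exit becomes a responder. The documents do not support that.

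**The follow-up text conflicts.** SAP 3.3.7 says disease assessments are not recorded after treatment discontinuation, and its table footnote limits this to stopping for an adverse event. Read literally, this could remove the exit evaluation too. The same section, however, also censors EFS at a last assessment that includes long-term follow-up, and SAP 3.3.9 has windows for that period. How much protection the worst-case collapse gives depends on which text governs.

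**Off-schedule response is part of the definition.** Protocol 14.1 and SAP 3.3.7 allow response at any evaluation, including unscheduled ones. That supports a response at some time. It does not make a Week 9 finding a 3-month rate, which is what SAP section 2 names.

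**The windows are ordinary midpoint windows.** Days 50-137 centre on (50+137)/2 = 93.5. This is true and suits the capture of failures. The difficulty is its combination with rule 4.

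**Other analyses help in part.** The Evaluable and Induction Phase Dosing Compliant populations exclude these subjects, but as secondary analyses and from numerator and denominator together. A subject who has left becomes a non-responder at the next visit under rule 3, and duration of response is censored at the last assessment. The inflation discussed here is therefore confined to the 3-month rate.

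**Later landmarks.** A reader might extend the point to them because their windows are equally wide. Whether exit tests are required there depends on the date of the previous evaluation. After an on-time Week 39 evaluation (Days 267-273), the 8-week exemption runs to Days 323-329, past the Day 319 opening of the Month 9 window. The documents do not establish a comparable effect, and no claim is made about it.

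**Conclusion.** The point holds in a narrow form. On the written rules, a subject is scored as a 3-month responder without being observed at 3 months if all of the following are true:

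- drug was stopped for a reason other than failure or recurrence;
- the exit evaluation was complete and clear before Day 78 (clearly so on Days 58-77; on Days 50-57 only if cytology was repeated);
- no later evaluation is recorded by Day 137.

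This assumes that the exit visit is recorded and handled as early-termination data. The bias is upward only.

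The number of such subjects is not given and cannot be derived, so the total effect is unknown. Each adds at most 1.3 points, and less in Cohorts 1+2. The 0.2 comparison only gives a sense of scale. It is the plan's precision target, which SAP 3.1 and protocol 17.8 tie to a 12-month rate, and not a stated success criterion for the 3-month rate.

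It would go too far to conclude that the primary result is materially inflated. What the documents show is a gap in the derivation rule that is cheap to close.

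**What to change.** 1. Keep Days 50-137 for capturing treatment failure at the 3-month visit.
2. Credit 3-month complete response only from an evaluation on or after Day 78. That is the start of Week 12, when the cytology is due, and 85-7 = 78 matches the allowance that protocol 10.5 gives maintenance visits: "a window of one week before and up to 2 weeks after these time points is permitted".
3. Extend rule 3 so that a subject who has discontinued treatment or study and has no evaluation on Days 78-137 is a non-responder at 3 months. Moving the window alone is not enough, because a subject who stopped drug but is still on study with no evaluation would remain a responder under rule 4.
4. Report the present wide-window result as a sensitivity analysis.
5. Reconcile the SAP 3.3.7 statement on assessments after treatment discontinuation with protocol 10.6 and 11.3 and with the SAP's long-term follow-up windows.

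A Day 78 opening still admits exit evaluations after a last dose from Day 41 (visit at 37 days) or Day 48 (visit at 30 days). That is defensible, because those subjects are seen at about 3 months. The rule is deliberately stricter for response than for failure, and the SAP should say so.

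The cost is SAP wording and one derivation rule, with no new data. The response rate may come out slightly lower.

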3.4. TIMING OF ANALYSES

A Data Safety Monitoring Board (DSMB) will review aggregated safety and limited efficacy data on a biannual basis.

An analysis of safety and limited efficacy data will be conducted once all subjects have completed 3, 6, and 12 months of follow-up.

A final analysis of all data will be conducted once all subjects enter the off-treatment period and the resulting data have been cleaned and quality assured, and the database locked.

4. ANALYSIS POPULATIONS

All reasonable efforts will be made to obtain complete assessment of all outcome measures for all subjects in the protocol. The following analysis populations will be evaluated:

4.1. ALL ENROLLED POPULATION

All enrolled population includes subjects who signed an informed consent form and were registered into the central enrollment system.

4.2. MODIFIED INTENT TO TREAT POPULATION

Modified Intent-to-Treat population includes subjects who received at least one dose of study medication. This is the primary population for efficacy and safety.

4.3. PRIMARY EFFICACY POPULATION

The primary efficacy population includes any subject in the mITT population with CIS. This will be the primary population utilized for the evaluation of complete response.

4.4. EVALUABLE POPULATION

The evaluable population includes any subject in the mITT population who completes the induction phase. This population will be used for secondary analyses of the efficacy endpoints.

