## **14.2 Criteria for Treatment Failure**

As defined in this protocol, the term “treatment failure” will refer to events that demonstrate the study drug Vicinium is not able to achieve or maintain a response in the subject’s bladder cancer. Specifically, the term “treatment failure” in this protocol is being used to define the following events:

1. Diagnosis at study entry was CIS (with or without papillary disease), high-grade Ta disease or high-grade T1 disease:

Subjects whose diagnosis at study entry was CIS or high-grade papillary disease will be considered to have a treatment failure if at the time of any disease status evaluation (per protocol every 13 weeks or any unscheduled evaluation) there is evidence of high-grade disease (CIS, high-grade Ta or high-grade T1 disease) or disease progression (e.g., to muscle invasive disease). Subjects who are found to have low-grade papillary disease at the time of evaluation must have the low-grade disease resected by TURBT. Low-grade disease is not considered a treatment failure in these subjects and they may remain on study treatment following TURBT.

2. Initial diagnosis was low-grade T1 disease:

Subjects whose initial diagnosis was low-grade T1 disease are considered to have a treatment failure if at the time of any disease status evaluation (per protocol every 13 weeks or any unscheduled evaluation) there is evidence of low-grade T1 disease, high-grade disease (CIS, high-grade Ta or high-grade T1 disease) or disease progression (e.g., to muscle invasive disease). Subjects whose initial diagnosis was low-grade T1 disease and who are found to have low-grade Ta disease at the time of evaluation must have the low-grade Ta disease resected by TURBT. Low-grade Ta disease is not considered a treatment failure in these subjects and they may remain on study treatment following TURBT.

3. Subjects with positive urine cytology without histologic, cytologic or radiographic evidence or upper or lower urinary tract malignancy will be considered as no longer in complete response and hence, as having a treatment failure.

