To evaluate biomarkers that may be associated with response or disease progression or treatment failure, which may include, for example, EpCAM status, tumor subtype morphology, furin levels in tumor cell endosomes, presence of a glycosaminoglycan coat, and presence of receptors that could impede a host anti-tumor immune response such as PD-L1.

3. **GENERAL STATISTICAL CONSIDERATIONS**

3.1. **SAMPLE SIZE AND POWER**

Assuming the true complete response rate at 12 months is 30%, sample sizes associated with various widths of a two-sided, exact (Clopper-Pearson) 95% confidence intervals are provided in the table below:

Sample Size (N)	Target Distance from P to Lower Limit	Proportion (P)	Lower Limit
121	0.080	0.300	0.220
95	0.090	0.300	0.210
76	0.100	0.300	0.200

Under the provided assumptions, a sample size of ≥ 77 evaluable subjects with early relapsed/refractory CIS with or without papillary disease is sufficient to estimate complete response rate with an exact 95% confidence interval that excludes 0.2 (PASS 2008).

The secondary endpoint of event-free survival (EFS) will be used to assess the treatment effect in all subjects, i.e., those with CIS (with or without papillary disease) and those with papillary-only disease. An estimate of EFS at the 18 month time-point will be calculated. The total sample size of 134 subjects will provide at least 80% power to test the null hypothesis that the event-free survival rate at 18 months is 20% versus the alternative hypothesis that the event-free survival rate at 18 months is $\geq 30\%$. This calculation is based on the assumptions of a nonparametric distribution for event-free survival and the length of follow-up is 24 months.

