EFS is defined as the interval from the date of first dose of study treatment to an event. Subjects who have a treatment failure or die following the post induction visit will be treated as having an event on the date of treatment failure or death. Subjects without evidence of a treatment failure who are diagnosed with upper or lower urinary tract urothelial carcinoma by histology, cytology or radiographic evidence will be censored at the date of diagnosis. Subjects without evidence of a treatment failure who undergo cystectomy will be censored at the date of cystectomy. All other subjects will be censored at the time of last assessment including long-term follow up.

Censoring rules for the analysis of EFS are presented in the table below.

Table: Censoring scheme for EFS

Situation	Date of Event or Censoring	Outcome
Treatment failure	Date of treatment failure	Event
Death without treatment failure and occurring prior to treatment discontinuation	Date of death	Event
Death without treatment failure and occurring after treatment discontinuation	Date of last evaluable disease assessment on or prior to treatment discontinuation ^a	Censored ^a
No baseline disease assessment	Date of first dose	Censored
No on-study disease assessments and no death	Date of first dose	Censored
No treatment failure and no death	Date of last evaluable disease assessment	Censored
New anti-cancer therapy received without treatment failure and reported prior to or on the same day as disease assessment	Date of last evaluable disease assessment on or prior to the date of initiation of subsequent therapy	Censored
Second non-NMIBC cancer reported prior to or on the same day as disease assessment	Date of last evaluable disease assessment on or prior to the date of diagnosis of non-NMIBC cancer	Censored
a This censoring rule acknowledges that disease assessments were not recorded after treatment discontinuation due to an AE.		

Cystectomy-Free Days

Cystectomy-free days is defined as the time from the date of first dose of study treatment to physical removal of the bladder. Subjects who are alive and do not have their bladder removed will be censored at the time of last contact.

Censoring rules for the analysis of cystectomy-free days are presented in the table below.

Table: Censoring scheme for Cystectomy

Situation	Date of Event or Censoring	Outcome
Cystectomy	Date of cystectomy	Event
Death without cystectomy	Date of death	Censored
No cystectomy	Date of last contact	Censored

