4.5. INDUCTION PHASE DOSING COMPLIANT POPULATION

The induction phase dosing compliant population includes any subject in the evaluable population who completes at least 85% of the dosing the induction phase. This population will be used for secondary analyses of efficacy endpoints.

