5.2.5. Additional Efficacy Analyses

The following analyses will be conducted in the mITT population, the evaluable population, the induction phase dosing compliant population, and the study dosing compliant population.

EFS will be estimated using the method of Kaplan-Meier. Subjects without evidence of a treatment failure who are diagnosed with upper or lower urinary tract urothelial carcinoma by histology, cytology or radiographic evidence will be censored at the date of diagnosis. Subjects without evidence of a treatment failure who undergo cystectomy will be censored at the date of cystectomy. All other subjects will be censored at the time of the last assessment. The ninety-five percent (95%) confidence interval around the EFS rate at 18 months will be presented.

Time to disease recurrence will be estimated separately for each cohort using the method of Kaplan-Meier. For subjects in Cohort 3, time to disease recurrence is defined as the number of days from first dose of study treatment to the first occurrence of treatment failure. Subjects who do not experience treatment failure will be censored at the last assessment.

Cystectomy-free days, time to progression, progression-free survival, and overall survival will be estimated based on the method of Kaplan-Meier.

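### Two secondary efficacy populations require completed induction while time still runs from first dose: CR, OS and cystectomy results in them are flattered, EFS and PFS only through early documented events

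*SAP*

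**What the plan says.** - **SAP 4.4:** "The evaluable population includes any subject in the mITT population who completes the induction phase". It gives the role of the set: "This population will be used for secondary analyses of the efficacy endpoints". It does not define what completing induction means.
- **SAP 4.5:** "The induction phase dosing compliant population includes any subject in the evaluable population who completes at least 85% of the dosing the induction phase".
- **SAP 5.2.5:** "The following analyses will be conducted in the mITT population, the evaluable population", followed by the induction phase dosing compliant and study dosing compliant populations. The endpoints are EFS, time to recurrence, cystectomy-free days, time to progression, PFS and OS. The table list in SAP 12 adds CR by visit and duration of response in the same sets (14.2.1.4, 14.2.1.5, 14.2.2.6, 14.2.2.7).
- **SAP 3.3.7:** "EFS is defined as the interval from the date of first dose of study treatment to an event". PFS, OS, cystectomy-free days and time to recurrence also start at first dose. No landmark is given for any population.
- **SAP 5.2.1:** "Patients who discontinue or die before Month 3 will be included in the denominator of the primary analysis". Subjects who have left the study and lack the data needed for response are non-CR.
- **Protocol 14.2:** failure is declared if, at any disease evaluation ("per protocol every 13 weeks or any unscheduled evaluation) there is evidence of high-grade disease"), or on disease progression. Protocol 11.3 then requires study drug to stop. It also requires this for cystectomy and unacceptable toxicity.

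**The concern.** A subject who has a cystectomy, dies, or has a failure documented at an unscheduled evaluation before the Week 12 dose cannot complete induction. That subject leaves the evaluable set although the outcome is known. SAP 3.3.9 assigns unscheduled findings from Study Day 50 onward to the post-induction visit. A failure found on Days 50 to 77 therefore counts as a post-induction failure in the primary analysis and is absent from the evaluable analysis.

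Because the clock starts at first dose, everyone left in the set is also credited with an induction period in which these events could not occur. Two of the four populations in SAP 5.2.5 are affected. The study dosing compliant population (SAP 4.6) is drawn from the mITT population and does not require completed induction. At stake is whether supportive tables look better than the mITT tables for reasons unrelated to the drug.

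**Working it through.** **1. The plan's own figure.** The documents give no figure for the evaluable set, so only the general sizing can be reproduced. With exact Clopper-Pearson limits at P = 0.30, the smallest N for a distance of 0.10, 0.09 and 0.08 to the lower limit is 76, 95 and 121, as in SAP 3.1. At N = 77, 23 responders give a lower limit of 19.97% and 24 give 21.1%.

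**2. Guaranteed time.** SAP 3.3.8 sets Week 12 at target Day 78, window Days 78 to 84. From Day 1 this is 78 - 1 = 77 days = 11.0 weeks, or 84 - 1 = 83 days = 11.9 weeks at the end of the window.

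**3. CR.** Let d be the share of dosed CIS subjects who do not complete induction. The documents do not give d; 5% to 15% is assumed. If none of them responds, the rate among completers is CR/(1-d):

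- d = 5%: 0.30/0.95 = 31.6%
- d = 10%: 0.30/0.90 = 33.3%
- d = 15%: 0.30/0.85 = 35.3%

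In counts, with 23 responders and 77 dosed (the Cohort 1 minimum):

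| Excluded | Rate | Exact 95% CI |
|---|---|---|
| 0 | 23/77 = 29.9% | 19.97% to 41.4% |
| 4 | 23/73 = 31.5% | 21.1% to 43.4% |
| 8 | 23/69 = 33.3% | 22.4% to 45.7% |
| 12 | 23/65 = 35.4% | 23.9% to 48.2% |

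The factor 1/(1-d) is the upper end. A subject who stops drug early but has a clean evaluation in the post-induction window can be a CR under SAP 5.2.1. The rate rises as long as those removed respond less often than those kept.

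**4. OS and cystectomy.** Let q be the share with the event before about Day 78 (not in the documents). If exactly these subjects are removed, S(t) becomes S(t)/(1-q). For a true 18-month value of 0.80, q = 1%, 2% and 5% give 0.808, 0.816 and 0.842.

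**5. EFS, PFS and recurrence.** The SAP 3.3.7 censoring tables treat early leavers as follows:

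- *No on-study assessment and no death:* censored at first dose. Such a subject adds nothing to the mITT curve, so removal changes nothing.
- *Death after treatment discontinuation without failure:* censored in mITT too.
- *On-treatment death, or failure or progression found at an unscheduled evaluation:* an event in mITT, absent from the evaluable set.

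Only the last group moves the curve. With 18-month EFS of 0.30 among completers, all dosed subjects have 0.30 × 0.98 = 0.294 at q = 2% and 0.30 × 0.95 = 0.285 at q = 5%. A Kaplan-Meier simulation under the SAP rules (N = 134, 400 runs per scenario) agrees. It gave 0.296 against 0.302 at q = 2% and 0.287 against 0.302 at q = 5%. At q = 0 the mITT and evaluable values were identical for drop-out of 0%, 10% and 20%.

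**6. Where failures are found.** Protocol 10 and 10.4 place the first scheduled evaluation at the end of induction: cytology in Week 12, cystoscopy in Week 13. A subject failing there has normally completed induction, stays in the evaluable set and counts as a failure.

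**The case against.** The strongest reply is that nothing decisive rests on these sets. The primary population is all dosed CIS subjects, early discontinuations and deaths stay in its denominator, and SAP 4.4 calls its own analyses secondary. SAP 5.2.2 gives estimates and intervals without a success rule, so crossing 20% in the evaluable set decides nothing. The 23/77 example is also knife-edge, since one more responder clears 20% in the full set. It uses the Cohort 1 minimum, whereas the SAP's primary CIS set combines Cohorts 1 and 2. All of this stands, and it limits the weight of the point.

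The documents' earlier trials do not suggest many early events. Phase 2 had no deaths and no AE discontinuations in 46 subjects. Phase 1 had one death in 64, three weeks after drug was stopped. Those schedules differed, but they are the only guide given. At q = 1% to 2%, a true 18-month EFS of 20% reads 20.2% to 20.4% (0.20/0.99, 0.20/0.98).

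A reader might infer three stronger claims that the documents do not support:

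- *Induction failures vanish from the denominator.* Most are found at the post-induction evaluation and remain.
- *Every endpoint is biased upward.* Drop-outs with no assessment and no death do not move EFS or PFS. The flat early EFS curve largely reflects the visit schedule and appears in mITT as well. It also rests on the SAP's dating of failures: protocol 17.5 would put post-induction failures at Day 1, but the SAP takes precedence.
- *The 20% benchmark is tied to the SAP 4.4 set.* SAP 3.1 says "evaluable subjects with early relapsed/refractory CIS with or without papillary disease is sufficient to estimate complete response rate", but protocol 17.8 also speaks of evaluable subjects and protocol 17.2 defines no such population. One word is ambiguous; no link is stated.

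The reply does not remove the selection itself. It is written into SAP 4.4, carried into 4.5, and planned for a full set of tables without a conditional label.

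**Conclusion.** The point holds in limited form and is a cheap improvement to secondary analyses. CR moves upward when non-responding early discontinuers are removed, by at most 1/(1-d): 30% reads 31.6% to 35.3% for an assumed d of 5% to 15%. OS and cystectomy curves lose every event in about the first 11 weeks. EFS, PFS and recurrence move only with documented early events, by about 0.6 points at q = 2% and 1.5 points at q = 5% on an 18-month EFS near 30%. Neither d nor q is in the documents, so the actual size is unknown. The direction for CR assumes that those removed respond less often than those kept. Nothing here supports the inference that the primary CR result is compromised.

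**What to change.** 1. **SAP 4.4:** define what completing induction means. Also keep mITT subjects who stop during induction because of treatment failure, progression, cystectomy or death, counted as non-CR or as events under the existing endpoint rules.
2. **CR:** present any completer-only rate as conditional on completing induction, with the number excluded and the reasons. This is needed even after step 1, because subjects who leave for adverse events or withdrawn consent remain outside the denominator. The primary analysis counts them as non-CR when response data are missing.
3. **SAP 4.5 and 5.2.5:** in any set that still requires completed induction, start EFS, PFS, OS, cystectomy-free days and recurrence at a post-induction landmark and label the result as conditional. SAP 3.3.7 dates a failure at its earliest component, which can be the Week 12 cytology. The landmark rule must therefore say that failures found at the post-induction evaluation count as events.
4. **SAP 3.1:** state that the 20% benchmark applies to the mITT-based primary efficacy population and not to the SAP 4.4 set.

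The cost is a few sentences and a changed start date in the affected tables, with no new data. The supportive figures become slightly less favourable, and landmark curves no longer share a clock with the mITT curves.
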